## 5.5 Drug Accountability

Ribociclib and letrozole are oral medications, patients will bring the containers to the visits for pill accountability, per section 5.2.

## 5.6 Concomitant Medications

Patients will be instructed to consult the Investigator or other appropriate study personnel before taking any new medications, supplements, or vaccines during the study prescribed by a provider or over the counter medications or supplements-.

Concomitant medications taken within 30 days prior to baseline will be recorded. At each study visit, all concomitant medications taken since the previous visit, including prescription and non-prescription medications, vitamin and mineral supplements, herbal and naturopathic remedies, vaccines, and supportive therapies, will be recorded.

### 5.6.1 Permitted Concomitant Medications

Medications required to treat AEs, manage cancer symptoms, concurrent diseases, and supportive care agents, such as pain medications, antiemetics, and antidiarrheals are allowed. Potential drug interaction between ribociclib and concomitant medications should always be taken into consideration when prescribing such medications. Bisphosphonates and denosumab are allowed.

Prophylactic use of WBC growth factors with ribociclib is not recommended.

Antiemetic therapy can be used according to clinical guidelines for antineoplastic medications with low to minimal emetogenic potential for treatment and/or prevention of nausea and vomiting as a result of study treatment

### **5.6.2 Medications Prohibited**

A full list of the medications that are prohibited during study treatment can be found in the [appendix 14.4](#).

Other investigational and anti-neoplastic therapies (including radiation) are prohibited.

Systemic corticosteroid treatment should not be given during the study treatment with ribociclib, except for:

- a. Topical applications (e.g. for rash), inhaled sprays (e.g. for obstructive airways diseases), eye drops or local injections (e.g. intra-articular)
- b. A short duration (< 5 days) of systemic corticosteroids  $\leq$  to the anti-inflammatory potency of 4 mg dexamethasone (e.g. for chronic obstructive pulmonary disease or as an antiemetic).

### **5.6.3 Medications Not Recommended**

In [appendix 14.5](#) there is a list of the medications are not recommended during study treatment and within 14 days prior to the first dose of study medication and for the duration of study treatment. These medications should be excluded if possible. If they must be given, then it will be based on the investigator's judgment.

## **6 Study Procedures**

### **6.1 Schedule of Events**

Screening assessments are to be conducted within 28 days prior to initiating protocol therapy unless otherwise specified. CBC with differential and biochemical profile (sodium, potassium, calcium, chloride, bicarbonate, BUN, creatinine, AST, ALT, total bilirubin, albumin, alkaline phosphatase) assessments must be done within 28 days prior to initiating protocol therapy, between day 8-16 of cycle 1, and prior to initiation of cycle 2.

Table 14. Study Calendar: Patients will be followed for one cycle

Study procedure/task	Screening a	Treatment cycle is 28 days	End of study b
Study day	≤ 28 days prior to study entry	Cycle 1 Day 8 - 16	
Procedures			
Eligibility criteria c	X		
Informed consent d	X		
Clinical visits e	X	Per routine clinical practice	
Adverse Events		X	X
CYP3A5 Screening f	X		
Treatments g			
Ribociclib		600 mg PO once daily for 21 days, followed by a 7-day rest period to complete a 28-day treatment cycle	
Fulvestrant		500 mg IM injection on days 1 and 15	
Letrozole		2.5 mg PO daily	
Goserelin		3.6 mg SQ every 28 days or 10.8 mg SQ every 12 weeks	
Leuprolide depot		3.75 mg IM every 28 days or 11.25 mg IM every 12 weeks	
Tests			
Blood draw for pharmacogenomic studies		X	
Serial blood draws for pharmacokinetic studies			

 
Immediately prior to the ribociclib dose, and 0.5hr ± 5min, 1hr ± 5min, 2hr ± 15min, 4hr ± 15min, 6hr ± 15min after the daily dose of ribociclib.
 
		X	
Electrocardiogram h	X	X	X
CBC with differential and CMP i	X	X	X
Pregnancy Test j	X		
NCI CTCAE PRO questionnaire k	X	X	X
Adverse event monitoring log	X	X	X
Medication adherence PROMIS questionnaire and drug accountability		X	X

a Screening: All assessments should be performed within 28 days prior to study entry. Study entry will be defined by confirmation of eligibility.

b This visit will occur prior to initiation of cycle 2 (e.g., 29th day of the study, plus or minus 3 days)

c Eligibility Criteria Evaluation: Patients must meet all of the eligibility criteria reported in the protocol

d Informed Consent: Must be obtained prior to undergoing any study-specific procedures.

e Clinical Visits: clinical visits will include medical history, vital signs and physical exam and will be conducted as per local practice and as clinically indicated. Physical Examination includes a general clinical examination of major body systems.

f To be performed after informed consent and used for screening according to sections 3.6 and 4.3.7. CYP3A5 Screening may be bypassed per Principal Investigator discretion if the necessary number of participants with each phenotype are enrolled (cohort of AA or Black participants - at least 3 poor metabolizers; cohort of NHW participants - at least 3 intermediate or normal metabolizers). If CYP3A5 is already performed it does not need to be repeated within the window of  $\leq$  28 days.

g All patients will receive ribociclib plus physician choice endocrine therapy with fulvestrant or letrozole. Luteinizing hormone-releasing hormone (LHRH) agonist (goserelin or leuprolide) will be required for premenopausal women.

h To be performed at these times per routine clinical practice and the treating physician: prior to treatment initiation; repeat on day 8-16 of cycle 1, and prior to initiation of cycle 2

i To be performed at these times per routine clinical practice and the treating physician: baseline, repeat on day 8-16 of cycle 1, and prior to initiation of cycle 2

j To be performed at these times per routine clinical practice and the treating physician: Pregnancy test (serum or urine), required for women of childbearing potential

k Questionnaires to be completed within 28 days of C1D1

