## 2.4 Secondary Endpoints

1. Ribociclib pharmacokinetic properties: maximum concentration ( $C_{max}$ ), the time to reach  $C_{max}$  ( $T_{max}$ ), AUC, clearance, volume of distribution( $v_d$ ), elimination half-life, and mean residence time (MRT) at steady state (visit between days 8-16 of cycle 1).
2. Change in QTc interval between:
  - 1) baseline and between days 8-16 of cycle 1,
  - 2) baseline and scheduled visit prior to initiation of cycle 2
3. Laboratory abnormalities: neutropenia, ALT, and AST, between
  - 1) baseline and between days 8-16 of cycle 1,
  - 2) baseline and scheduled visit prior to initiation of cycle 2

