- Alanine transaminase (ALT)  $< 2.5 \times \text{ULN}$ , except for patients with liver metastases, who are only included if the ALT is  $< 5 \times \text{ULN}$ .
- Alkaline phosphatase  $\leq 2.5 \times \text{ULN}$  ( $\leq 5.0 \times \text{ULN}$  if bone metastases present)
- Patient must have the following laboratory values within normal limits or corrected to within normal limits with supplements, or are not clinically significant per the Investigator:
  - Sodium
  - Potassium
  - Calcium
- The following tests are not necessary. However, if results are available, values should be as follows:
  - INR  $\leq 1.5$  (unless the patient is receiving anticoagulants and the INR is within the therapeutic range of intended use for that anticoagulant within 7 days prior to the first dose of study drug).
  - Magnesium within normal limits or corrected to within normal limits with supplements, or is not clinically significant per the Investigator.
- Standard 12-lead electrocardiogram values defined as (obtained from baseline electrocardiogram):
  - QTc interval at screening  $< 450 \text{ ms}$  (using Fridericia's correction)
  - Mean resting heart rate  $\geq 50 \text{ bpm}$  (determined from the electrocardiogram)

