- Patient has any other concurrent severe and/or uncontrolled medical condition that would in the investigator's judgment, cause unacceptable safety risks to the patient, contraindicate patient participation in the clinical study, or compromise compliance with the protocol.
- Patient has clinically significant, uncontrolled heart disease or who are at significant risk of developing QT prolongation, including any of the following:
  - Documented myocardial infarction (MI), angina pectoris, coronary artery intervention, or pericarditis within 6 months prior to study entry
  - Documented cardiomyopathy, congestive heart failure, valvular heart disease, congenital heart disease, or prior cardiac surgery
  - Left Ventricular Ejection Fraction (LVEF) < 50% (testing is not mandatory)
  - Personal diagnosis of long QT syndrome, cardiac channelopathies, family history of idiopathic sudden death, congenital long QT syndrome or channelopathies
  - Personal risk factors for Torsades de Pointe (TdP) including uncorrected hypokalemia, hypomagnesemia, or need for concomitant medications with a known risk to prolong the QT interval and/or known to cause TdP that cannot be discontinued or replaced by safe alternative medication (e.g. within 5 half-lives or 7 days prior to starting study drug, whichever is longer)
  - Clinically significant cardiac arrhythmias or conduction abnormalities, including, but not limited to ventricular tachycardia, atrial tachyarrhythmia, left bundle branch block, right bundle branch block, QRS prolongation (greater than 120 ms), intraventricular conduction delay, high-grade AV block (e.g. bifascicular block, Mobitz type II and third-degree AV block)
  - Uncontrolled hypertension
  - Inability to determine the QTc interval
- Patient is currently receiving any of the following substances and cannot be discontinued 7 days prior to Cycle 1 Day 1:
  - Concomitant medications, herbal supplements, and/or fruits that are strong inducers or inhibitors of CYP3A4/5 (section 5.6).
  - Medications that have a narrow therapeutic window and are predominantly metabolized through CYP3A4/5 (section 5.6).
  - Chronic dosing of corticosteroids such as dexamethasone and prednisone is known to lead to induction of CYP3A enzymes, thereby potentially reducing ribociclib drug exposure to sub-therapeutic levels. Systemic corticosteroid treatment should not be given during the study treatment with ribociclib, except for:

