- Topical applications (e.g. for rash), inhaled sprays (e.g. for obstructive airways diseases), eye drops or local injections (e.g. intra-articular)
  - A short duration (< 5 days) of systemic corticosteroids ≤ to the anti-inflammatory potency of 4 mg dexamethasone (e.g. for chronic obstructive pulmonary disease or as an antiemetic).
  - Medications that prolong the QTc interval (section 5.6).
- Inability to comply with study requirements.
- Psychiatric illness or social situation that would limit compliance with study requirements.
- Patients with clinically significant liver disease, including active viral or other known hepatitis, current alcohol abuse, or cirrhosis.
- Known active hepatitis B (defined as having a positive hepatitis B surface antigen [HBsAg]) or known active hepatitis C (defined as a positive test for hepatitis C viral load by polymerase chain reaction [PCR]).
  - Patients with past hepatitis B virus (HBV) infection or resolved HBV infection (defined as having a negative HBsAg test and a positive antibody to hepatitis B core antigen [anti-HBc] antibody test) are eligible.
  - Patients with positive hepatitis C antibody AND negative quantitative hepatitis C by PCR AND no clinical/laboratory evidence of cirrhosis are eligible. Patients who have completed curative therapy for HCV are eligible if they meet all other parameters for enrollment.
  - Patients are not required to undergo testing for HBV or HCV for enrollment.
- Known uncontrolled HIV infection defined as any of the following criteria:
  - CD4 counts ≤ 350 cells/µL; or
  - HIV viral load ≥ 400 copies/mL; or,
  - Have been taking an antiretroviral regimen for < 4 weeks prior to treatment with study drugs, if anti-retroviral therapy is deemed necessary or appropriate by the investigator.
  - Patients are not required to undergo testing for HIV for enrollment.

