#### **4.3.9 Electrocardiogram**

Electrocardiograms will be obtained prior to the first cycle, middle of the first cycle (between C1D8-C1D16), at prior to the initiation of the second cycle. During the study, electrocardiogram will be assessed by the treating physician. If there are grade 2-4 cardiac toxicities the patient will be referred to cardio-oncology. At the end of the study cardio-oncology will review and tabulate results of QTc interval in all electrocardiograms (three per patient: one at baseline, cycle 1 day 8-16 and prior to initiation of cycle 2).

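### The baseline ECG for QTc change need not follow the stop of a QT-prolonging drug, so in a patient who stops one the change from baseline can be biased downward

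*Combined protocol and SAP*

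**What the plan says.** **Endpoint.** Section 2.4 lists "Change in QTc interval between" baseline and days 8-16 of cycle 1, and between baseline and the visit before cycle 2. Section 9.2 compares the change from baseline to C1D8-C1D16 between CYP3A5 metabolizer groups by t-test or Wilcoxon test, and also models QTc change by regression.

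**ECGs.** Section 4.3.9 counts "three per patient: one at baseline, cycle 1 day 8-16 and prior to initiation of cycle 2". Table 14 footnote h gives their timing as "prior to treatment initiation; repeat on day 8-16 of cycle 1, and prior to initiation of cycle 2", and leaves them to routine practice and the treating physician. Section 6.1 sets the window: "Screening assessments are to be conducted within 28 days prior to initiating protocol therapy unless otherwise specified". Under section 3.3 the same baseline ECG supplies the QTcF value for eligibility (below 450 ms).

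**Stopping other QT drugs.** Section 3.4 excludes as follows: "Patient is currently receiving any of the following substances and cannot be discontinued 7 days prior to Cycle 1 Day 1". QTc-prolonging drugs are on the list that follows. For known-risk drugs, the Torsades de Pointes item adds an interval: "e.g. within 5 half-lives or 7 days prior to starting study drug, whichever is longer". Both intervals count back from the start of treatment, not from the ECG. Section 3.6.1 requires eligibility to hold up to the first treatment day but orders no repeat ECG.

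**The concern.** A change score is only as good as its baseline. If the baseline is recorded on a QT-prolonging drug that has gone by the later visits, the change combines two things: what ribociclib adds and what the withdrawn drug no longer contributes. The second has a known sign, so the error is a bias and not just noise.

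Two uses of the baseline are at stake. One is the secondary endpoint, and through it the comparison of QTc change between genotype groups. The other is the Table 7 rule that permanently stops ribociclib for a rise above 60 ms from baseline with signs of serious arrhythmia: a raised baseline makes that rise harder to reach. The absolute QTcF limits in Table 7 do not use the baseline.

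**Working it through.** The documents give no power or precision figure for QTc change, so there is no stated number to reproduce. The check is of timing, then of size.

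**1. Can a compliant baseline precede the stop?** The window is 28 days before therapy (6.1). The latest permitted stop under the 7-day rule is day -7 (3.4). For a drug stopped then, 28 - 7 = 21 of the 28 days (75%) come before the stop. These are calendar days, not a probability. Footnote a of Table 14 counts the window from study entry instead, which could lengthen it. So the answer is yes: an ECG at day -20 with a stop at day -7 breaks no rule.

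**2. How long is the other drug gone at the later ECGs?** From day -7 to C1D8 is 7 + 7 = 14 days. To day 29 it is 7 + 28 = 35 days.

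**3. How much ribociclib is present before cycle 2?** The last dose is on day 21 (5.3.1), the visit is day 29 plus or minus 3 (Table 14 footnote b), and the half-life is 32 hours (1.2.2).
- Day 29: 8 × 24 = 192 h; 192/32 = 6 half-lives; 0.5^6 = 1.6% left.
- Day 26: 120/32 = 3.75 half-lives; about 7% left.
- Day 32: 264/32 = 8.25 half-lives; about 0.3% left.

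On schedule, this ECG is nearly free of ribociclib.

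**4. What does each contrast measure?** Let B be the drug-free QTc, d the withdrawn drug's effect, R the ribociclib effect at day 8-16, and e the small residual effect before cycle 2. Assume first that d has gone by the later visits.
- Day 8-16 minus baseline = (B + R) - (B + d) = R - d. This understates R by d.
- Pre-cycle 2 minus baseline = (B + e) - (B + d) = e - d. This is mainly the loss of the other drug.
- Day 8-16 minus pre-cycle 2 = R - e. Here d cancels.

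If a fraction r of d remains at the later ECG, the error in the first two is d(1 - r).

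**5. Shift in a group mean.** Shift = k × d / n, for k affected patients among n. The values of d are assumptions. The group sizes come from section 3.3: cohorts of 18, with genotype groups of 3 and 15 at the quota limits. Pooling cohorts at those limits gives 3 + 15 = 18 per phenotype. Section 9.2 does not say whether the QTc comparison is pooled or within cohort.

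| Affected / group size | d = 5 ms | d = 10 ms | d = 20 ms |
|---|---|---|---|
| 1 of 18 | 0.3 | 0.6 | 1.1 |
| 2 of 18 | 0.6 | 1.1 | 2.2 |
| 1 of 15 | 0.3 | 0.7 | 1.3 |
| 1 of 3 | 1.7 | 3.3 | 6.7 |

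**The case against.** The strongest reply is that the case is rare and partly recoverable. A patient must be on a QT-prolonging drug, have QTcF below 450 ms while on it, have the ECG before stopping, and then stop. The documents give no count. Section 5.6 records co-medication from 30 days before baseline, so such patients can be found. The covariate list in section 9.2 is open-ended, so a stopped QT drug could be added to the regression. All of this stands, and it keeps the point small. It does not remove it: the planned two-group test uses the unadjusted change, no such covariate is named, and analysis cannot retime an ECG.

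A reader might infer more than the documents support:
- *That the change is lost for good once ribociclib starts.* It is not. Step 3 shows that the scheduled pre-cycle-2 ECG is a near-drug-free reference, although a single tracing.
- *That both later ECGs understate ribociclib in the same way.* Only the day 8-16 ECG is on treatment.
- *That entry safety is weakened.* A baseline taken on the other drug makes the 450 ms limit harder to meet, so the screen is conservative.
- *That section 3.4 is unworkable because section 5.6 leads to two QT lists.* The neighbouring items in 3.4 match rows of Appendix 14.4, and 5.6.3 allows Appendix 14.5 drugs on judgment, so 14.4 is the natural reading. The two stop intervals are cumulative and do not conflict. A 14.5 drug continued throughout acts at every ECG and causes no such bias.

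**Conclusion.** The gap is real: the plan allows the only baseline ECG to be recorded on a QT-prolonging drug that must then be stopped, and no section orders a later one. In an affected patient, QTc change to day 8-16 is too small by about the withdrawn drug's effect, and the change to pre-cycle 2 mostly reflects that withdrawal. One such patient shifts a mean by 0.3 to 1.1 ms in a group of 18, which is minor, or by 1.7 to 6.7 ms in a genotype group of 3.

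These figures rest on an assumed effect of 5 to 20 ms and on near-complete loss of the other drug by the later ECG. The near-drug-free status of the last ECG also assumes dosing on schedule, the 32-hour half-life, and a QTc effect that follows concentration. The number affected may be zero, and the primary AUC comparison is untouched. It is a cheap correction to consider, not a defect that threatens the trial.

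**What to change.** 1. Add to Table 14 footnote h: *If a prohibited QT-prolonging drug (Appendix 14.4) is stopped during screening, the baseline ECG used for QTc change is taken after the section 3.4 stop interval and before the first ribociclib dose; C1D1 before the dose is acceptable.* The end-of-study tabulation in 4.3.9 should then use that ECG as baseline.
2. For patients already measured, report QTc change with and without those whose co-medication record shows a QT drug stopped after the baseline ECG. For those patients, also show day 8-16 minus pre-cycle 2.

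The cost is one sentence and a later, or occasionally repeated, ECG in the few patients who stop such a drug. The wording covers only the ECG used for QTc change, so an earlier screening ECG can still serve eligibility. The sensitivity analysis needs no new data. The drug lists, the stop intervals in 3.4 and the 14-day advice in 5.6.3 can stay as they are.

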## 6.2 Patient Withdrawal

Patients may withdraw from the study at any time at their own request, or they may be withdrawn at any time at the discretion of the investigator for safety or behavioral reasons, or the inability of the patient to comply with the protocol required schedule of study visits or procedures at a given study site.

Reasons why patients may discontinue or be withdrawn from the protocol may be due to the following:

- AEs
- Intercurrent illness
- Disease progression
- Patient is non-compliant
- Patient is lost to follow-up
- Withdrawal of consent

If a patient does not return for a scheduled visit, every effort should be made to contact the patient. In any circumstance, every effort should be made to document patient outcomes, if possible. The investigator should inquire about the reason for withdrawal, request the patient to return all unused investigational product, request the patient to

return for a final visit, if applicable, and follow up with the patient regarding any unresolved AEs.

## 7 Assessments

### 7.1 Safety Assessments

Safety assessment will consist of monitoring of all AEs, including serious adverse events (SAEs) at every clinical visit and monitoring of hematology to be performed to check the patient's eligibility at the time of screening, on day 8-16 of cycle 1, and prior to initiation of cycle 2

Other procedures as necessary according to standard of care and in accordance with each site's institutional guidelines will be assessed to monitor for AEs related to the underlying disease, treatment with ribociclib, other endocrine therapy, or supportive therapies.

#### 7.1.1 Physical Examination

A full physical examination of all major body systems will be required at screening. Symptom directed physical examinations will be performed as per routine clinical practice during the study. Only physical examination at screening will be recorded on the case report form (CRF).

#### 7.1.2 Safety Assessments

Blood tests will include the following:

- 1) Hematology panel: complete blood count with differential
- 2) Blood chemistry panel: ALT, ASL, alkaline phosphatase, total bilirubin, serum creatinine

Blood tests will be drawn at the time points described in the study calendar table and analyzed at local laboratories.

A hematology panel (includes complete blood count with differential) will be performed to verify the patient's eligibility at screening, repeat on day 8-16 of cycle 1, and prior to initiation of cycle 2. Laboratory data will be recorded on the CRF.

Blood Chemistry will be performed to verify the patient's eligibility at screening, repeat on day 8-16 of cycle 1, and prior to initiation of cycle 2. Laboratory (blood chemistry and

hematology panels) data will be recorded on the CRF. In the case a laboratory abnormality meets the definition of AE, as determined by the investigator and according to AE reporting, this must be captured on an AE CRF page.

Electrocardiograms will be performed to verify the patient's eligibility at screening, repeat on day 8-16 of cycle 1, and prior to initiation of cycle 2 of treatment with ribociclib. Data will be recorded on the CRF. In the case an electrocardiogram abnormality meets the definition of AE, as determined by the investigator and according to AE reporting, this must be captured on an AE CRF page.

